4.6.2 Maternal Secondary Outcomes

1. Preterm birth < 37 weeks (major secondary outcome)
2. Indicated preterm birth < 37 weeks
3. Preterm birth < 34 weeks
4. Preeclampsia with severe features as defined by the ACOG diagnostic criteria (i.e., severe hypertension, thrombocytopenia, impaired liver function, progressive renal insufficiency, pulmonary edema, new-onset and persistent cerebral or visual symptoms)
5. Postpartum preeclampsia diagnosed after 48 hours
6. Gestational hypertension defined as new onset hypertension in the absence of accompanying proteinuria or other features of preeclampsia
7. Pregnancy associated hypertension (gestational hypertension or preeclampsia)
8. Gestational diabetes
9. Adherence to study medication
10. Adverse Events of Special Interest (AESI) defined as myalgia and muscle weakness, and serious AESI defined as maternal myositis, myopathy, rhabdomyolysis, and serious liver injury
11. Gestational age at delivery
12. Length of hospital stay for the delivery admission and number and length of maternal hypertension related and overall hospitalizations during the pregnancy
13. Concentrations of angiogenic factors (sFlt-1, sEng, and PIgf)
14. Concentrations of cholesterol (total, low density lipoprotein, high density lipoprotein) and triglycerides
15. A composite of severe maternal morbidity of either maternal death, eclampsia, HELLP syndrome, cerebral vascular accident, heart failure, myocardial infarction, acute respiratory distress syndrome requiring mechanical ventilation, disseminated intravascular coagulopathy, pulmonary edema, renal failure, liver rupture, or placental abruption

4.6.3 Fetal and Neonatal secondary outcomes

1. Fetal and neonatal death
2. Birth weight and rate of “small for gestational age” as measured by birth weight: a) < 5 th percentile and b) < 10 th percentile for gestational age, assessed specifically by sex and race of the infant based on United States birth certificate data^{110,111}
3. Admission to neonatal intensive care unit/intermediate nursery and total length of stay in that unit
4. Complications of prematurity including:
 - a. Mechanical ventilation in the first 72 hours of life and duration
 - b. Oxygen support and duration

- c. Respiratory distress syndrome (RDS), defined as the presence of clinical signs of respiratory distress (tachypnea, retractions, flaring, grunting, or cyanosis), with an oxygen requirement and confirmed by a chest x-ray
- d. Bronchopulmonary dysplasia (BPD), defined as oxygen requirement at 28 days of life and at 36 weeks corrected gestational age
- e. Necrotizing enterocolitis (NEC), defined as modified Bell Stage 2 (clinical signs and symptoms with pneumatosis intestinalis on radiographs) or Stage 3 (advanced clinical signs and symptoms, pneumatosis, impending or proven intestinal perforation)
- f. Intraventricular hemorrhage (IVH) grade III-IV
- g. Periventricular leukomalacia (PVL), diagnosed by neuroimaging
- h. Retinopathy of prematurity (ROP) stage III or higher
 - i. Neonatal sepsis (within 72 hours and > 72 hours after birth). The diagnosis of sepsis will require the presence of a clinically ill infant in whom systemic infection is suspected with a positive blood, CSF, or catheterized/suprapubic urine culture; or, in the absence of positive cultures, clinical evidence of cardiovascular collapse or an unequivocal radiograph confirming infection.
 - j. Composite outcome of: fetal or neonatal death, RDS, Grade III-IV IVH, PVL, Stage 2 or 3 NEC, BPD, Stage III or higher ROP, or early onset sepsis
 - k. Seizures
- 5. Congenital anomaly / birth defect (excluding any conditions that must have been present before randomization)
- 6. Neonatal auditory brain stem response (ABR)/ Otoacoustic Emissions (OAE)

4.6.4 Child Secondary Outcomes

- 1. Body mass index for age at 24 corrected months and 5 years of age using CDC pediatric growth charts
- 2. Cognitive, Language and Motor Scale Scores from the Bayley Certified Scales of Infant Development 4 at 24 months age
- 3. Level from the Gross Motor Function Classification System at 24 months of age
- 4. Hearing loss or vision problems (severe nearsightedness or farsightedness, and eye movement problems) at 24 months of age
- 5. Total problems score and syndrome scale (emotionally reactive, anxious/depressed, somatic complaints, withdrawn, attention problems, aggressive behavior) scores from the Child Behavior Checklist at 24 months and 5 years of age
- 6. General Conceptual Ability score and subscale (verbal ability, non-verbal reasoning ability, and spatial ability) scores from the Differential Ability Scales at 5 years of age
- 7. Global Executive Composite score and index (behavioral, emotion, and cognitive regulation) scores from the Behavior Rating Inventory of Executive Function at 5 years of age
- 8. Adaptive Behavior Composite score and domain (communication, daily living skills, socialization and motor skills) scores from the Vineland Adaptive Behavior Scale at 5 years of age
- 9. Visual acuity and strabismus from visual assessment at 5 years of age

4.7 Adverse Event Reporting

Detailed information concerning adverse events will be collected and evaluated throughout the conduct of the protocol.

Any maternal death, neonatal death, life threatening maternal event or Serious Adverse Event of Special Interest as defined in Section 4.5 must be entered into the adverse events database within twenty-four hours of being notified. If a death is reported, a copy of the patient's de-identified medical record will be uploaded to the adverse events database.

Adverse events which do not qualify under the above definition must be entered into the database within 7 days of being notified.

4.8 Emergency Unblinding

The only indication for breaking the randomization code is when it is medically necessary to unmask the study drug assignment to be able to treat the patient, i.e. when treatment options would differ based on the knowledge of the medication. In such a situation, the center should try to contact the BCC before unmasking but in an emergency situation, the PI of the center, the Nurse Coordinator, the alternate PI or the site PI may authorize the unmasking.

5 Data and Safety Monitoring Plan

5.1 Data and Safety Monitoring Committee

The Data and Safety and Monitoring Committee (DSMC) for the *Eunice Kennedy Shriver National Institute of Child Health and Human Development (NICHD) Maternal-Fetal Medicine Units (MFMU) Network* is an independent group appointed by the NICHD to oversee MFMU Network trials. The primary objective of the DSMC is to ensure the safety of study subjects and to provide NICHD, and for this study, NHLBI with advice on the ethical and safe progression of the trial. The DSMC also advises the Institutes on research design issues, data quality and analysis, as well as ethical and human subject aspects of studies. Recommendations will be made to the NICHD and NHLBI and disseminated to the Steering Committee.

5.1.1 DSMC Membership Qualifications

The DSMC members are appointed by the Director of NICHD in accordance with established NIH policies governing the use of advisors. DSMC members are chosen for their expertise in one or more of the following fields:

- Maternal-fetal medicine or obstetrics
- Neonatology
- Ethics
- Biostatistics/epidemiology
- Clinical trial methods

One of the members with expertise in obstetrics or maternal-fetal medicine is appointed as Chairperson. In addition, a layperson or member of the public is appointed as a patient advocate.

In addition to the members of the DSMC, an NICHD representative who is not part of the MFMU Network is appointed as a liaison between the Institute and the committee. NHLBI may also appoint a representative. The NIH representatives participate in the deliberations, but do not vote.

5.1.2 Conflict of Interest and Confidentiality

Members of the DSMC may not be affiliated with any of the clinical centers or the BCC and must be financially and intellectually independent of the trial investigators. As part of their service on the Committee, members must sign an annual conflict of interest and confidentiality declaration. If a new conflict arises for a member, it must be disclosed in a timely manner (within 30 days) to the NICHD. The NICHD will determine whether the conflict limits the ability of the DSMC member to participate in the committee.

All data and information remain confidential. Interim data analysis reports and any other reports provided to DSMC by the BCC must be returned or destroyed. Investigators from the MFMU Network will not communicate directly with DSMC members about the study except when making presentations or responding to questions regarding review of a protocol during a DSMC meeting or scheduled conference call.

5.1.3 Responsibilities of the DSMC

Specifically, the responsibilities of the DSMC members are as follows:

Before the start of the trial:

- To review the research protocol and informed consent document(s) with respect to ethical and safety standards. The study design should be evaluated to determine whether it is adequate to answer the research question(s).

While the trial is ongoing:

- To evaluate whether the study design assumptions are valid and the impact of the assumptions on how well the research question(s) will be answered.
- To monitor the safety of the participants including review of serious adverse events as they arise.
- To monitor recruitment, losses to follow-up, compliance with the protocol by investigators and participants, and data quality.
- To monitor the evidence for treatment harm or benefit and to evaluate evidence for treatment differences in the main efficacy outcome measures.
- To assess the impact and relevance of external evidence on the advisability of trial continuation as well as on the need for design modification including the necessity for modification of the informed consent material.
- To make recommendations for changes to the study design, if necessary, to ensure that the research question(s) will be answered.
- To recommend continuation or termination of a trial for all participants, certain treatment groups, or certain participant subgroups.

5.2 Protocol Review

Before the start of the trial, the DSMC reviews the final protocol and provides comments. The Chair of the Protocol Subcommittee or designee may present the protocol, and be available to answer questions. The subcommittee Chair will report the DSMC's comments to the Steering Committee for consideration and possible modification of the protocol. The trial cannot start until the DSMC approves the protocol. Approval is by consensus.

If the Steering Committee proposes major changes to the protocol during the course of the trial (e.g. eligibility criteria), the DSMC must review and approve the changes before they can go into effect, provided that the DSMC has not already been unblinded to study treatment in an interim analysis.

5.3 Ongoing Safety Monitoring

As described in Section 4.7 any maternal death, neonatal death, life threatening maternal event or serious Adverse Event of Special Interest (myositis, myopathy, rhabdomyolysis or serious liver injury as defined in Section 4.5) is reported electronically within twenty-four hours of notification. Other adverse events are reported within seven days of notification. The BCC is automatically notified by the adverse event system of the addition of a new adverse event. BCC staff review each report for completeness before passing it on to the NICHD – approved medical monitor. The medical monitor reviews the adverse event reports including the accuracy of the classification of seriousness, unexpectedness and relatedness to the study interventions. The medical monitor is masked to treatment assignment.

The adverse events reports are then forwarded electronically to the DSMC Chair, the NIH representative(s) to the DSMC, and any other DSMC member who requests notification. Deaths, life threatening events, serious Adverse Events of Special Interest and SUSARS (see below) are reported immediately. Other adverse events are forwarded on a monthly basis. The DSMC Chair decides whether the adverse event reports should be disseminated to the rest of the committee, whether a follow-up call or meeting is required, and whether the treatment assignment should be unmasked. If NIH or the Steering

Committee is concerned about a pattern of events, they may request that the DSMC consider their concern.

An FDA Investigational New Drug (IND) safety report will be completed and forwarded to the FDA for any serious unexpected suspected adverse reaction (SUSAR) to the study medication that is fatal or life threatening (whether active or placebo) within 7 days after the event was entered into the database. For other adverse events classified as SUSAR, notification will be reported to the FDA within 15 days. All cumulative adverse events will be reported in the annual IND report.

Finally, cumulative adverse events are reported to the DSMC at each meeting and will be considered along with other interim safety data in the DSMC deliberations.

5.4 Data and Safety Monitoring Committee Meetings

For this study the DSMC will meet at least every six months, once in person and once most likely by conference call. The committee may meet more often as needed. DSMC meetings and conference calls are organized into open and closed sessions, and if requested, an executive session. Definitions for each of the session types are included below.

- Open session – Open sessions are attended by the NICHD Project Scientist, the NHLBI Project Scientist if desired and may be attended by Steering Committee member(s), or the Steering Committee Chairperson as requested by NICHD Project Scientist.
- Closed session – Closed sessions are attended only by the NICHD (and NHLBI representative if desired), the BCC PI, and BCC personnel involved in the trials being monitored. The Project Scientist(s) do not attend the closed session. For closed session conference calls, the BCC will provide participants with the dial-in information shortly before the call.
- Executive session – An executive session may be requested at any time by the committee. Only the full voting members, appropriate ad hoc members of the DSMC, and NICHD/other Institute DSMC representatives attend. BCC staff do not attend the executive session.

Meetings will always be scheduled to include the DSMC Chair and a biostatistician. A quorum of this DSMC is considered to be two-thirds of the full members (i.e. not including the NIH representatives). Agreement is reached by consensus.

5.4.1 Study Report to the DSMC

For the bi-annual meeting, and any other meeting called by the DSMC to review data, a report will be generated by the BCC in advance. Data are presented by treatment group and by center. For security purposes, the treatment groups will be coded in the report (e.g. A or B). The decision to unmask the treatment group at the meeting is at the discretion of the DSMC. A full report on a study that has accrued sufficient patients to evaluate outcome will include the following:

- Enrollment data
- Baseline data
- Compliance and side effects
- Adverse events
- Protocol adherence, including data quality, data completeness, and timeliness
- Primary outcome
- Secondary outcomes

- Additional study specific information as requested by the DSMC

However, the main emphasis is on the primary outcome as well as maternal safety outcomes (including maternal myositis, myopathy, rhabdomyolysis and serious liver injury).

5.4.2 Interim Analysis

Two special interim analyses will be performed to review the maternal and neonatal safety outcomes by treatment group. The first after the first 50 women randomized have delivered and the second after the first 310 women randomized (20%) have delivered. After each of these special interim analyses, the DSMC will make the recommendation to continue the 20mg dose or lower the dose to 10mg.

Given that the sample size estimates involve a number of assumptions, it is planned that the assumptions and the resulting primary outcome rate in the placebo group be examined after the first 310 women randomized have delivered. The DSMC would be charged with making a recommendation regarding potential revision of the sample size.

Once the first 50% of the patients have been accrued into the trial and delivered, the report also will include a formal interim analysis evaluating the primary outcome by treatment group on this cohort of patients. A second interim analysis will be performed after 75% of the patients have been accrued and delivered. Each cohort consists of all patients randomized before a certain date so that the analysis cohort does not depend on gestational age at delivery. Additional interim analyses of the primary outcome will be at the discretion of the DSMC.

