5.4.3 Trial Stopping Rules

For the primary outcome, the group sequential method of Lan and DeMets will be used to characterize the rate at which the type I error is spent.¹¹² This method is flexible with regard to the timing of the interim analyses. Asymmetric stopping boundaries will be used. The upper boundary which describes the stopping rule for benefit will be based on 1-sided type I error of .025 and the Lan-DeMets generalization of the O'Brien-Fleming boundary. The lower boundary will be based on a less stringent stopping rule: 1-sided type I error of .05 and the Lan-DeMets generalization of the Pocock type boundary.

It is also planned to calculate conditional power given the observed data to date, and conditional on the future data showing the originally assumed design effect. If this conditional power is low (under 10 percent) the DSMC may consider termination for futility if the accrual rate is slow, with confidence that the Type II error is not greatly inflated.¹¹³

Specific stopping rules for the trial will be established for monitoring maternal, neonatal and child events relevant to pravastatin risk. For the maternal stopping rule, an occurrence of one of the following events will qualify:

- Serious Adverse Event of Special Interest (serious AESI; myositis, myopathy, rhabdomyolysis or serious liver injury as defined in Section 4.5).
- Non-serious AESI (myalgia or muscle weakness as defined in Section 4.5) that required repeat discontinuation of study medication (initial discontinuation, rechallenge, discontinuation again)

For the neonatal stopping rule the following event will qualify:

- Failed newborn ABR/OAE test

The BCC will continuously monitor these maternal and neonatal events and if there is an excess of women in the pravastatin group who have experienced one or more of the events such that the one sided nominal p-value of a Fisher's exact test is less than 0.05 or such that the lower 90% confidence bound of the relative risk exceeds 1.0 for larger sample sizes of 50 or more, will request that the DSMC review the

data immediately and make a determination on stopping or pausing the trial, or modifying the dose. Likewise if there is an excess of neonates who have failed their hearing tests, the same stopping criteria will apply.

For the child stopping rule, the following events will qualify:

- Cognitive or Motor Scale Score < 70 (2.5th percentile) from the Bayley Certified Scales of Infant Development 4 at 24 months age

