6.2 Sample Size and Power

In all of the older studies, except the High Risk Aspirin study, aspirin was not being used routinely. In the High Risk Aspirin trial, the dose was lower than is generally used today and was started later in gestation. Therefore, for the purposes of sample size estimation, it is conservatively assumed that all women will be receiving low dose aspirin, and that the rate of preeclampsia (primary outcome) in the placebo group is 20%. It is estimated that a sample size of 1,550 women is required to demonstrate at least a 30% reduction in preeclampsia with the use of pravastatin (from 20% to 14%), with a power of 85%, and type I error of 5% 2-sided. The sample size is adjusted for a drop-out rate of 5% (i.e. that 5% of the women on pravastatin discontinued their study drug and had the same primary outcome rate as the placebo group) and for the interim 'looks' at 50% and 75% information.

Table 5. Sample Sizes for Different, Levels of Power and Effect Sizes

Reduction in Primary Outcome Rate	Power %	Estimated Sample Size
25%	80	2000
	85	2280
	90	2660
30%	80	1360
	85	1550
	90	1810
35%	80	980
	85	1120
	90	1290

Trials evaluating cardiovascular disease event rates have reported that the combination of pravastatin and aspirin consistently has greater efficacy than pravastatin or aspirin alone indicating at least an additive and possibly a synergistic effect.¹¹⁹ Therefore, there is minimal concern that concomitant aspirin use would reduce the effect size.

Preterm birth < 37 weeks of gestation is considered to be the major secondary outcome. With a sample size of 1550, there is more than 80% power to detect an effect as small a 20% reduction in preterm birth.

The sample size for this study is also sufficient to detect with at least 80% power a 40% reduction in preterm delivery < 34 weeks and a 30% reduction in NICU/special care admission.

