9.2.2 Estimate of Recruitment Rate

There are more than 160,000 deliveries per year in the MFMU network which would result in 800 potentially eligible women (160,000 x 0.5%). Assuming that 80% of the women delivering at MFMU network centers would be available for screening (i.e. that they present for care early enough in gestation, at clinics that are accessible and do not meet exclusion criteria), and that 50% of these women consent (a conservative consent rate for studies involving high risk patients in the Network) it is estimated that approximately 320 patients per year or 26-27 patients will be enrolled per month. The first 50 women will be enrolled over 6 months. Recruitment of the remaining 1500 women will take approximately 4.8 years.

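### Does the sample-size review at 310 women need a written formula and limits before it is used?

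*Combined protocol and SAP*

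**What the plan says.** Section 5.4.2 schedules the review at 20% of the planned 1,550 women, once that group's deliveries are complete: "it is planned that the assumptions and the resulting primary outcome rate in the placebo group be examined after the first 310 women randomized". On the outcome of the review it says: "The DSMC would be charged with making a recommendation regarding potential revision of the sample size". The review therefore covers the design assumptions as well as the placebo-arm rate. Those assumptions are in Section 6.2: a 20% placebo rate, a 30% reduction (20% to 14%), 85% power, two-sided 5% error, 5% drop-out modelled as dilution, and looks at 50% and 75% information.

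On what the committee sees, Section 5.4.1 says "Data are presented by treatment group and by center", with the groups coded. It lists the primary outcome in the full report once enough patients have accrued to evaluate it, and adds: "The decision to unmask the treatment group at the meeting is at the discretion of the DSMC". The formal comparison of the primary outcome by arm is planned at 50% and 75% only, with further looks at the DSMC's discretion (Section 5.4.2). In Section 5.4.3, "The upper boundary which describes the stopping rule for benefit will be based on 1-sided type I error of .025", with O'Brien-Fleming type spending. Nothing there refers to a revised N.

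**The concern.** Three things look wrong at first.

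- **Missing rule.** No formula is written, and Section 5.4.2 does not say which effect is kept, whether N may fall, or how far it may move.
- **Noisy input.** The named rate rests on one arm of 310 women, so chance alone could point to a much longer or much shorter trial.
- **No explicit firewall.** Reading a placebo rate requires the placebo code to be identified, and with the total it also yields the pravastatin rate. Lan-DeMets spending copes with changes in the timing of looks. It does not protect the error rate when the maximum N is chosen after the arm difference has been seen.

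At stake are the benefit-side error rate, the length of the trial, and the ability to show afterwards that N did not follow the interim result.

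**Working it through.** **The plan's own figure.** With a pooled-variance two-proportion formula at two-sided 5% and 85% power, 20% against 14% needs 1,406 women. With 5% of the pravastatin arm at the placebo rate, the treated rate is 0.95 × 14% + 0.05 × 20% = 14.3%, and N becomes 1,568, within 1.2% of 1,550. Adding the inflation for the looks (× 1.019) gives 1,598. Power at 1,550 is then 83.9%, about a point below the stated 85%. The planned N is not in dispute.

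**Noise in the placebo rate.** 310 women at 1:1 is about 155 on placebo. SE = √(0.20 × 0.80 / 155) = 0.0321, so the 95% range is 0.20 ± 1.96 × 0.0321, or 13.7% to 26.3%.

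**Translation into N.** Scale from 1,550 with f(p, q) = [p(1−p) + q(1−q)] / (p−q)², where f(0.20, 0.14) = 0.2804 / 0.0036 = 77.89. The scaling is an assumption of this check.

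| Observed placebo rate | 30% relative reduction kept | 6-point difference kept |
|---|---|---|
| 13.7% | 1,550 × 121.32 / 77.89 ≈ 2,414 | 1,550 × 52.58 / 77.89 ≈ 1,050 |
| 26.3% | 1,550 × 55.27 / 77.89 ≈ 1,100 | 1,550 × 98.78 / 77.89 ≈ 1,970 |

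The direction reverses with the effect that is kept. Section 6.2 mentions both forms, but Table 5 is indexed by relative reduction, and the power statements for the secondary outcomes are relative too. The left-hand column is therefore the natural reading. At the 320 women per year of Section 9.2.2, it means (2,414 − 1,550) / 320 × 12 ≈ 32 months longer or (1,550 − 1,100) / 320 × 12 ≈ 17 months shorter.

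**Error under a mechanical rule.** Assumptions: N follows the placebo rate within 775 to 3,100; looks fall at 50%, 75% and 100% of the revised N with critical values 2.963, 2.359 and 2.014; null rates run from 16% to 25%. Simulated benefit-side error is about 2.7%. With the same critical values applied symmetrically, harm-side error is about 2.3%, and the total is 4.98% to 5.03%. A rule based on the pooled rate gives 2.5% on the benefit side.

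**Worst case.** For each interim z at 310 women, take the N that maximises the chance of a false claim of benefit, then average over the null distribution. Fixed N returns 2.50%, as it should.

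| Permitted N | Largest benefit-side error |
|---|---|
| 1,550 to 2,410 | 2.74% |
| 1,550 to 3,100 | 2.85% |
| 1,100 to 2,410 | 2.97% |
| 775 to 3,100 | 3.39% |
| 640 to 6,200 | 3.83% |

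**What each rule buys.** Power and mean N before any early stopping, at 20% against 14.3%. The pooled rate is divided by 0.8575 = (0.20 + 0.143) / 2 / 0.20 to recover a placebo rate.

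| Rule | Power | Mean N |
|---|---|---|
| N fixed at 1,550 | 84.1% | 1,550 |
| Placebo rate, up or down | 86.8% | 1,601 |
| Placebo rate, floor 1,550 | 88.3% | 1,702 |
| Pooled rate, up or down | 84.1% | 1,581 |
| Pooled rate, floor 1,550 | 86.2% | 1,661 |

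At a 16% placebo rate with a 20% reduction, power is 50.6% with the placebo rate (up or down), 46.7% with the pooled rate and 39.0% with N fixed. At a 25% rate with a 30% reduction, a floor forgoes a saving: mean N is 1,553 to 1,561, against 1,192 to 1,204 without it.

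**The case for a change.** The strongest case for a change is that a rule costs one paragraph and cannot be added credibly once arm data have been seen. Reports by arm may begin before 310 women, at the six-monthly meetings and the 50-woman safety review. At 310 women the committee also reviews safety by arm, and it may call extra analyses of the primary outcome. Without limits on N, the worst-case error has no fixed ceiling: a simpler calculation with one final test at 1.96 and N anywhere from 320 to 12,000 reaches 5.4% one-sided.

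The silence on limits stands, and so does the point that a placebo rate reveals more than a pooled one. The rest carries less weight. The named quantity is a rate, not a difference, and the arms are coded. The output is a recommendation: Section 1.3 requires Steering Committee and IRB approval of protocol changes and their submission as IND amendments, and Section 5.5 requires detailed minutes. Section 5.2 makes DSMC approval of major Steering Committee changes depend on the DSMC not already having been unblinded. That clause covers a different route, so it protects only in part, but it shows that the risk was considered. Section 1.3 also mentions a manual of operations, which is not available here, so a rule held there cannot be excluded.

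**Conclusion.** No change is needed. Section 5.4.2 leaves a detail unstated that analysts can fill sensibly by recomputing Section 6.2 at the observed placebo rate with the 30% reduction kept. Following the plan that way does not produce a wrong result: two-sided error stays at about 5.0%, and power rises by 86.8 − 84.1 = 2.7 points for 1,601 − 1,550 = 51 more women on average. The 3.4% figure is an upper limit for N within 775 to 3,100 and requires a deliberate choice of N from the arm difference. The wide range of N is sampling noise in an early estimate, which is a reason to leave judgement to an advisory committee and not to bind it. Placebo or pooled rate, floor or no floor, is a trade-off with no option best in every scenario examined.

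This rests on 155 women per arm, the scaling from 1,550, and symmetric boundaries for the two-sided total. The plan's actual harm boundary is a one-sided 0.05 Pocock type, so its harm-side error will differ. The conclusion would weaken if the DSMC in fact set N from the observed difference, but nothing in the plan provides for that.
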